4.4. Permanent Discontinuation of Study Therapy

An individual subject will not receive any further investigational product if any of the following occur in the subject in question:

Withdrawal of consent or lost to follow-up

Adverse event that, in the opinion of the investigator or the sponsor, contraindicates further dosing

Subject is determined to have met one or more of the exclusion criteria for study participation at study entry and continuing investigational therapy might constitute a safety risk

Pregnancy or intent to become pregnant

Any AE that meets criteria for discontinuation as defined in Section 9.3.

- Serious Adverse event related to thoracic radiation, with the exception of toxicities that do not meet the criteria for discontinuation as defined in Section 9.3.
- Dose-limiting toxicity (See Section 6.3 for definition of DLT).
- Grade ≥ 3 infusion reaction

18 Nov 2020 Page **64** of **164**

- Subject noncompliance that, in the opinion of the investigator or sponsor, warrants withdrawal; e.g., refusal to adhere to scheduled visits
- Initiation of alternative anticancer therapy including another investigational agent
- Confirmation of PD and investigator determination that the subject is no longer benefiting from treatment with durvalumab
 + tremelimumab

Subjects who are permanently discontinued from further receipt of investigational product, regardless of the reason (withdrawal of consent, due to an AE, other), will be identified as having permanently discontinued treatment.

Subjects who are permanently discontinued from receiving investigational product will be followed for safety per Section 9.0 and Appendix 2 or 3, including the collection of any protocol-specified blood specimens, unless consent is withdrawn or the subject is lost to follow-up or enrolled I another clinical study. All subjects will be followed for survival. Subjects who decline to return to the site for evaluations will be offered follow-up by phone every 3 months as an alternative.

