3.1.2. Determination of Eligibility

After eligibility is established, the study staff will register participants. The following are required to be submitted for successful registration:

Registration forms 🔛

Copy of subject consent 🔛

Copies of the following documents:

- Diagnostic pathology report(s) [SEP]
- PET/CT or CT scan report, MRI or CT brain with contrast report
- Laboratory reports including: [stp]

o Complete blood count (CBC) with differential (including absolute lymphocyte count) and direct platelet count.

18 Nov 2020 Page **55** of **164**

- o Chemistry: Albumin, SGOT (AST), SGPT (ALT), Bilirubin (direct and total), Calcium, Creatinine, Glucose, Total protein, Urea nitrogen, Uric Acid, Electrolytes (including sodium, potassium, chloride and bicarbonate).
- o Liver function tests (AST, ALT, Total bilirubin, alkaline phosphatase)
- o Urinalysis (routine)
- o Baseline thyroid immune safety assay: Thyroid Stimulating Hormone (TSH). Abnormal endocrine results should be followed up per standard of care, and may require an endocrine consult and additional testing.
- o Pulmonary function report
- o Other documents, if requested.

Study treatment cannot begin until the patient is registered. Subjects who sign a consent form, but do not initiate protocol treatment for any reason (e.g., subjects who are screen failures), will be replaced and will not count towards our accrual goal. Also patients who do not stay enrolled through the DLT period, will be replaced and not count towards our accrual goal.

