6.3. Definition of Dose Limiting Toxicity (DLT)

Dose-limiting toxicities (DLTs) will be evaluated from the first day of administration of durvalumab (cohort 1) or durvalumab+tremelimumab (cohort 2), in this trial. The period for evaluating DLTs will be from the day of first administration of study therapy until 30 days after surgical resection or 100 days following the last dose of study therapy, whichever occurs later. Subjects who do not remain on the study up to this time for reasons other than DLT will be replaced with another subject. Grading of DLTs will follow the guidelines provided in the Common Terminology Criteria for Adverse Events (CTCAE) version 4.0. A patient who experiences a DLT will be permanently discontinued from treatment and will proceed to surgery after standard preoperative evaluation by a surgeon and anesthesiologist. Prior to surgery any treatment related toxicity should have resolved to ≤grade 1. [5]

A DLT will be defined as any Grade 3 or higher toxicity that occurs during the DLT evaluation period. Toxicity that is clearly and directly related to the primary disease or to another etiology is excluded from this definition. The following will be DLTs:

- Any Grade 4 irAE
- Any ≥ Grade 3 colitis
- Any Grade 3 or 4 non-infectious pneumonitis irrespective of duration
- Any Grade 2 pneumonitis that does not resolve to ≤ Grade 1 within 3 days of the initiation of maximal supportive care
- Any Grade 3 irAE, excluding colitis or pneumonitis, that does not downgrade to Grade 2 within 3
 days after onset of the event despite optimal medical management including systemic
 corticosteroids or does not downgrade to ≤ Grade 1 or baseline within 14 days
- Liver transaminase elevation > 8 × ULN or total bilirubin > 5 × ULN
- Any ≥ Grade 3 non-irAE, except for the exclusions listed below

The definition excludes the following conditions:

- Grade 3 fatigue lasting ≤ 7 days
- Grade 3 endocrine disorder (thyroid, pituitary, and/or adrenal insufficiency) that is managed
 with or without systemic corticosteroid therapy and/or hormone replacement therapy and the
 subject is asymptomatic
- Grade 3 inflammatory reaction attributed to a local antitumor response (e.g., inflammatory reaction at sites of metastatic disease, lymph nodes, etc.)
- Concurrent vitiligo or alopecia of any AE grade
- Grade 3 infusion-related reaction (first occurrence and in the absence of steroid prophylaxis) that resolves within 6 hours with appropriate clinical management

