12.1. Study Design

This is an open-label pilot study aimed at establishing the safety and feasibility of neoadjuvant immunoradiation prior to surgical resection of stage III NSCLC, that is deemed surgically resectable by a thoracic surgeon with lobectomy. Thoracic RT will be given at standard doses and fractionation to a total dose of 45Gy in 25 fractions, as per published phase III data⁴⁹, and using standard methods. In cohort 1, the safety and feasibility of durvalumab with concurrent thoracic RT, will be assessed. In this cohort, durvalumab will be administered at the standard dose of 1500mg IV every 4 weeks for 3 doses, as per ongoing phase III studies. If preliminary safety is established in cohort 1, the study will expand to include cohort 2, which will test the safety and feasibility of durvalumab plus tremelimumab with concurrent thoracic RT. In this cohort, durvalumab will be administered at the standard dose of 1500mg IV every 4 weeks for 3 doses, and tremelimumab will be administered at the standard dose of 75mg every 4 weeks for 3 doses. The primary endpoints of this study are safety and feasibility in cohort 1 and cohort 2 (if applicable). Patients will be observed for perioperative grade 3-4 adverse events through day 90 following the last dose of immunotherapy or until 30 days post-surgery, whichever is longer. Safety and feasibility will be monitored continuously throughout the study through weekly meetings with investigators, as well as the planned Bayesian monitoring rules (see below). A set of markers of immune reactivity measured in lung tumor resection specimens, draining lymph nodes, and peripheral blood will be evaluated. Feasibility will be evaluated as the proportion of evaluable patients who successfully complete preoperative treatment and proceed to surgery without any extended treatment related delays. Extended treatment-related delay will be defined as >8 weeks from the day of completion of thoracic RT. For each cohort, we aim to accrue 16 evaluable patients, defined as those who receive at least one dose of durvalumab or durvalumab/tremelimumab administration and have complete toxicity follow-up. We plan to accrue 20 patients to ensure 16 evaluable patients are available for analysis. If less than 16 evaluable patients are available after accruing 20 patients, we will amend the protocol to ensure at least 16 evaluable patients are available for analysis.

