12.2. Study Endpoints Definition

12.2.1. Primary Endpoints

Safety of durvalumab monothererapy (cohort 1) +/- durvalumab+tremelimumab (cohort 2) administered preoperatively together with thoracic radiation in stage III NSCLC.

Safety will be measured by the frequency of any of the following events:

• Drug-related adverse events occurring up to 100 days after the last dose of immunotherapy or 30 days after surgery (whichever is longer).

18-Nov-2020 Page **114** of **164**

- Serious adverse events occurring up to 100 days after the last dose of immunotherapy or 30 days after surgery (whichever is longer).
- Clinical laboratory test by worst toxicity grade (as assessed at the time intervals outlined in the Schedule of Assessments, Figure 1.)

Feasibility of preoperative administration of durvalumab monothererapy (cohort 1) +/- durvalumab+tremelimumab (cohort 2) concurrently with thoracic radiation in stage III NSCLC

Feasibility will be evaluated through the proportion of evaluable patients who successfully complete preoperative treatment and proceed to surgery without any extended treatment-related delays defined as >8 weeks from the last day of thoracic radiation.

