12.2.2. Safety Endpoint

Safety stopping rule:

To minimize the risks of adding durvalumab monotherapy (cohort 1) or durvalumab+tremelimumab (cohort 2) to thoracic radiation prior to surgery, safety will be monitored by a Bayesian stopping rule for the rate of adverse events of interest (Section 9.2). Previous experience with single and multiple dose schedules of durvalumab and durvalumab+tremelimumab demonstrated that the incidence of grade 3-4 toxicities in advanced NSCLC and other solid tumors is low. The primary DLTs of concern for safety monitoring will be grade 3-4 toxicities of the types listed in section 6.3. These include liver, GI, renal, pneumonitis and any other grade 3-4 toxicity that in the opinion of the investigator significantly interfered with the subjects' optimal perioperative management. They will be monitored continuously for sixteen patients through day 90 following the last dose of immunotherapy (or day 30 post-surgery, whichever is longer).

AEs will be monitored continuously for all patients. A Bayesian safety monitoring rule will be used to evaluate the rate of the AE of interest continuously, from the 3rd evaluable patient, and will suspend accrual at any point if there is sufficient evidence of excessive toxicity. Specifically, the Bayesian toxicity monitoring rule will suspend accrual anytime if the posterior probability of AE of interest being larger than 25%, is 70% or higher. We assume a priori that the experimental regimens has an average risk around 5% and there is about 7% chance that the risk will be 25% or higher. This corresponds to a Beta (0.05,0.95) prior distribution. Table 10.1 summarizes the continuous stopping rule for the 16 evaluable patients for each regimen. For example, if 2 patients out of the first 3 or 4 evaluable patients experience adverse events of interest, we will stop accrual. Furthermore, to cautiously assess the toxicity profiles of experimental regimens in the event that accrual is relatively "fast" comparing to the safety assessment duration, the accruals of each cohort will be suspended when 6 eligible patients have been accrued to allow the continuous safety evaluations to be done among the first 6 evaluable patients before further accruals. The accrual would resume only if the following Bayesian stopping rule being used is not met. At any time if the stopping criterion is met, accrual to the trial will be temporarily suspended and the

18-Nov-2020 Page **115** of **164**

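### Section 4.4 lets safety follow-up end inside the DLT window when a patient off study drug joins another study; this conflicts with 3.1.6.2 and 9.3.1, and later events can be lost from the DLT rate

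*Combined protocol and SAP*

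**What the plan says.** Section 4.4 lists the reasons for permanently stopping study drug. They include adverse events, DLT, confirmed progression and the start of other anticancer therapy. Patients stopped in this way are followed for safety "unless consent is withdrawn or the subject is lost to follow-up or enrolled I another clinical study". Survival follow-up continues for everyone.

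Section 6.3 runs the DLT period from the first dose "until 30 days after surgical resection or 100 days following the last dose of study therapy, whichever occurs later". Section 12.2.1 uses the same end point for drug-related AEs and for SAEs.

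Three rules decide who is counted:
- Section 6.3: "Subjects who do not remain on the study up to this time for reasons other than DLT will be replaced with another subject".
- Section 3.1.2: "Also patients who do not stay enrolled through the DLT period, will be replaced and not count towards our accrual goal". It makes no exception for DLT.
- Section 12.1 aims for 16 evaluable patients per cohort, "defined as those who receive at least one dose of durvalumab or durvalumab/tremelimumab administration and have complete toxicity follow-up". It makes no exception for DLT either.

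Other sections bear on how long events are collected. Section 3.1.6.2 has the records of all who start therapy reviewed weekly to the end of the window, and seeks information from outside physicians when perioperative care moves elsewhere. Section 9.3.1 records AEs and SAEs through follow-up, and follows SAEs to resolution or stabilisation even after participation ends. Section 9.3.10 points the other way: SAE reporting runs to 90 days after the last dose or until alternative anticancer therapy starts.

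**The concern.** A patient who is reachable and still consents can stop being observed for safety because of a step that is plausibly linked to outcome. Patients who stop for progression, or for toxicity short of a DLT, are the ones likely to look for another trial. Once their follow-up is incomplete, they are replaced under 3.1.2 and 6.3 and are not evaluable under 12.1. The safety rule and the DLT proportion would then rest on patients who did not take that route. If the leavers go on to have more DLTs than the stayers, the observed rate is too low.

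The stakes are highest early. Accrual in each cohort pauses at six patients for the safety evaluation, and cohort 2 opens only once cohort 1 is judged safe.

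**Working it through.** **1. Reproduce the plan's figures.** The inputs come from Section 12.2.2: "This corresponds to a Beta (0.05,0.95) prior distribution", and the rule is to "suspend accrual anytime if the posterior probability of AE of interest being larger than 25%, is 70% or higher", applied from the 3rd to the 16th evaluable patient. After k DLTs in n patients the posterior is Beta(0.05 + k, 0.95 + n − k). The prior mean is 0.05/(0.05 + 0.95) = 5% and the prior P(rate > 25%) is 7.0%, both as stated.

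Applying the rule at every n gives this boundary: 2 DLTs at n = 3–4, 3 at 5–7, 4 at 8–11, 5 at 12–14 and 6 at 15–16. (Table 10.1 prints no column for 5 DLTs; that is a separate point.) An exact binomial recursion over this boundary gives:

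| True DLT rate | 0.15 | 0.20 | 0.25 | 0.30 | 0.35 |
|---|---|---|---|---|---|
| Stop, Table 10.2 | 15.8% | 29.3% | 43.1% | 60% | 72.8% |
| Stop, recomputed | 16.3% | 29.3% | 44.3% | 59.4% | 72.8% |

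All five agree within 2 points, so the recomputed rule is used below.

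**2. How much of the window can go unobserved.** Assume radiation ends about day 35 (25 fractions, 5 per week). Surgery 6–8 weeks later falls on days 35 + 42 = 77 to 35 + 56 = 91. Take a patient who stops after dose 2 (day 30) and, instead of surgery, enrols elsewhere at about that time. The window ends on day 30 + 100 = 130. Between 130 − 91 = 39 and 130 − 77 = 53 days are then unobserved.

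**3. What one unseen DLT does.** Posterior P(rate > 25%):
- n = 6: 0.841 with 3 DLTs (suspend); 0.552 with 2 (continue).
- n = 16: 0.818 with 6 DLTs (suspend); 0.641 with 5 (continue).

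**4. Effect on the stopping probability.** The documents give no rate of leaving for another study, so these are assumptions. Let a share w leave with no DLT yet recorded and be replaced. Let their DLT risk over the rest of the window be R times the stayers' risk. If the true rate under full follow-up is P, the stayers' rate, which is the one observed, is P/(1 − w + wR). With P = 0.30 (59.4% stop under full follow-up):

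| Share leaving | R = 1 | R = 2: rate, stop | R = 3: rate, stop |
|---|---|---|---|
| 5% | no change | 0.286, 55.2% | 0.273, 51.3% |
| 10% | no change | 0.273, 51.3% | 0.250, 44.3% |
| 20% | no change | 0.250, 44.3% | 0.214, 33.4% |

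For example, 0.30/(0.90 + 0.10 × 2) = 0.273. At P = 0.25 with 10% leaving and R = 2, the observed rate is 0.25/1.10 = 0.227 and the stopping probability falls from 44.3% to 37.3%.

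**The case against.** A reader might infer that patients who leave because of toxicity drop out of the co-primary safety data. The documents do not support that. Section 6.3 replaces only those who leave for reasons other than DLT. No text deletes events already recorded, and Section 12.3.1 tabulates AEs by type, grade and attribution for each regimen. The silence of 3.1.2 and 12.1 on DLT leavers is an inconsistency to repair; it does not show that those patients are removed.

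A reader might also infer that joining an observational study ends follow-up. Section 4.4 does not separate study types, but exclusion criterion 3 allows concurrent enrolment in an observational study, so that reading is strained.

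The strongest objection is that the plan elsewhere asks for continued collection: 3.1.6.2 and 9.3.1 as described, and 6.2.2.5 and 6.2.3, which keep some replaced patients in safety follow-up. This stands as evidence of intent, and it makes the problem a conflict between sections. It does not remove the problem. None of these passages overrides the explicit exception in 4.4, and none returns a replaced patient to the evaluable set.

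The clause is also narrow. It covers patients permanently discontinued, and arguably not those who completed three doses. Patients stopped for a DLT or a dosing delay are directed to surgery, which makes early entry into another trial less likely.

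Large effects are hard to defend. Suppose the true rate is 25%, and 30% of patients destined for a DLT and 5% of the rest leave first. Then 0.25 × 0.30 + 0.75 × 0.05 = 11.25% go by this one route, against about 10% planned drop-out from all causes (Section 14.3). The 10% rows in the table use up that whole allowance. A doubled risk is also demanding, because a leaver has only the rest of the window at risk. With R below 1 the same formula would push the observed rate up.

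**Conclusion.** The point holds as a conflict with a possible downward bias. As written, 4.4 allows safety follow-up to end inside the primary safety window on enrolment in another study, while 3.1.6.2 and 9.3.1 continue it. A site that follows 4.4 can miss later DLTs, AEs and SAEs, mainly after progression or toxicity short of a DLT, and the replacement and evaluability rules then take those patients out of the 16.

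The size cannot be established from the documents. It is nil at equal risk. At a true rate of 30% with twofold risk in leavers, the stopping probability falls from 59.4% to 55.2% if 5% leave and to 51.3% if 10% leave. These figures assume that leavers go with no DLT recorded and are replaced. In cohorts of 16, a single missed event is enough to change a suspension decision.

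**What to change.** - In 4.4, remove enrolment in another study as a reason to end AE and SAE follow-up within the 6.3 window, or limit it to study-specific procedures such as research blood draws. Withdrawal of consent remains a reason.
- Reconcile 9.3.10 with this. Otherwise SAE reporting can still end when alternative therapy starts, and changing 4.4 alone would not close the gap.
- Align 3.1.2, 6.3 and 12.1 so that any treated patient with a DLT counts as evaluable, whatever the later follow-up.
- Record the start date of any new agent and list later events separately.
- Report the DLT proportion in all treated patients beside the evaluable-set result.

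The cost is an amendment touching five sections and a few more telephone or chart contacts, of a kind already provided for in 3.1.6.2. Attribution becomes harder once a new agent has started; the separate listing makes that visible.

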4.5. Withdrawal of Consent

Subjects are free to withdraw from the study at any time (IP and assessments) without prejudice to further treatment.

Subjects who withdraw consent for further participation in the study will not receive any further IP or further study observation, with the exception of follow-up for survival, which will continue until the end of the study unless the patient has expressly withdrawn their consent to survival follow-up. Note that the patient may be offered additional tests or tapering of treatment to withdraw safely.

A subject who withdraws consent will always be asked about the reason(s) for withdrawal and the presence of any AE. The Investigator will follow up AEs outside of the clinical study.

If a patient withdraws consent, they will be specifically asked if they are withdrawing consent to:

- all further participation in the study including any further follow up (eg, survival contact telephone calls)
- withdrawal of consent to the use of their study generated data
- withdrawal to the use of any samples

18 Nov 2020 Page **65** of **164**

4.6. Replacement of Subjects

If subject withdraws from the study, that subject will be replaced.

4.7. Registration Procedures: General Guidelines

Eligible patients will be entered on study centrally at the Sidney Kimmel Comprehensive Cancer Center at the Johns Hopkins University by the CROCC Lead Study Coordinator. All sites should call/email the coordinating center at [contact] for registration. The Registration Form and Eligibility Worksheet will be supplied to each participating site.

Subjects who sign a consent form, but do not initiate protocol treatment for any reason (e.g., subjects who are screen failures), will be replaced and will not count towards our accrual goal. The Coordinating Center should be notified as soon as possible.

4.8. Registration Process

To register a patient, the following documents should be completed by the Research Nurse or Study Coordinator and emailed to [contact] and the CROCC Lead Study Coordinator to the Coordinating Center:

- Registration Form
- Signed patient consent form
- Eligibility Screening Checklist
- Copy of required screening tests (e.g., vitals, labs, EKGs) and scans

Study treatment cannot begin until the patient is registered. The Research Nurse or Study Coordinator at the participating site will then e-mail ([contact] and the CROCC Lead Study Coordinator) the Coordinating Center to verify eligibility. To complete the registration process, the Coordinating Center will:

- Assign a patient study number
- •Register the patient on the treatment portion of the study
- •Email confirmation of enrollment and the patient study number to the participating site

18 Nov 2020 Page **66** of **164**

5. Investigational Product(s)

